4.7.1.1 Immunosuppressive Medications During the Screening Period

Subjects that have previously been taking immunosuppressive medications (including but not limited to, AZA and MMF) and steroids not specifically excluded in Section 4.1.3 for the prevention or treatment of NMO/NMOSD relapses may continue to take those medications during the screening period as long as the dose remains stable or decreases.

Immunosuppressive medications must be stopped prior to dosing on Day 1. Steroids must continue according to the protocol (see Section 4.5.2.2).

4.7.2 Prohibited Concomitant Medications

The following medications (and procedure) are prohibited from the day of dosing on Day 1 through the end of the subjects' participation in the OLP:

- Any immunosuppressant for the prevention of NMO/NMOSD attacks (this includes but is not limited to AZA, MMF, rituximab, etc)
- High-dose steroids, with the exception of those required to treat an NMO/NMOSD attack
- Low-dose steroids, unless discussed and agreed with the medical monitor, with the exception of those specified by the protocol in the RCP and topical steroids
- PLEX, unless used to treat an NMO/NMOSD attack.
- Alemtuzumab
- Eculizumab
- Total lymphoid irradiation
- Bone marrow transplant
- T-cell vaccination therapy
- Natalizumab
- Cyclosporin
- Methotrexate
- Mitoxantrone
- Cyclophosphamide
- Tocilizumab
- Any other immunosuppressant medication, unless discussed and approved by the medical monitor

In addition to the medications described above, subjects must be instructed not to take any medications, including over-the-counter products, without first consulting with the investigator.

Subjects may exit the OLP at any time for any reason, including seeking alternative treatment options, at which point they will enter the SFP.

There are no prohibited medications during the SFP. During the SFP, a subject may receive standard treatment for their NMO/NMOSD at the discretion of the investigator and in compliance with established clinical practice.

4.8 Statistical Evaluation

4.8.1 General Considerations

Tabular summaries will be presented by treatment group. Categorical data will be summarized by the number and percentage of subjects in each category. Continuous variables will be summarized by descriptive statistics. Additional details of statistical analyses will be described in the statistical analysis plan.

The primary and key secondary endpoints will be analyzed and reported based on both AQP4-IgG seropositive and Intent-to-Treat (ITT) population, defined as all subjects who are randomized into the study and receive at least one dose of investigational product. Additional efficacy analyses will be performed in both seropositive and ITT populations. Treatment groups will be analyzed according to the initial randomization, regardless of whether subjects receive an investigational product different from that to which they were randomized.

The safety data will be presented using the as-treated population, which will include all subjects who receive any investigational product. Specifically, subjects who received all placebo doses will be included in the placebo group for safety analyses; conversely, subjects who received at least one dose of MEDI-551 will be included in the active treatment group for safety analyses.

Efficacy and safety data from the OLP will be presented based on subjects who receive at least one dose during the OLP.

Unless otherwise specified, all statistical inference will be done at a significance level of two-sided $\alpha = 0.05$.

4.8.2 Sample Size and Power Calculations

The current study is being planned to detect a target relative reduction of 60% in risk for time from Day 1 to onset of an AC-determined NMO/NMOSD attack on or before Day 197 with 90% power and $\alpha = 0.05$ (two-sided). Details are provided in Appendix 9. A total of 67 AC-determined NMO/NMOSD attacks are required for the ITT population. Subjects will be randomized in a 3:1 ratio to receive either MEDI-551 or placebo within both AQP4-IgG seropositive and seronegative strata. The stratification ratio is anticipated to be approximately 80:20 with higher allocation to the seropositive cohort. If the seropositive cohort has 80% of the attacks, the study will have approximately 82% power to detect the target relative reduction of 60%.

A maximum of 252 subjects will be randomized and dosed in this study. Because this study is event-driven where the primary objective is based on a total of 67 AC-determined NMO/NMOSD attacks, and the rate of NMO/NMOSD attacks is not established in the literature, this number of subjects was determined by analyzing masked data of the actual

attack rate from the first 78 subjects who completed the RCP in this study. The attack status (attack/no attack) of the 78 subjects was randomly sampled with different attack rate which gave an estimate of the number of attacks for the total sample size. This simulation process was repeated 10,000 times to give a distribution of the number of attacks for the total sample size, from which the probability of observing at least 67 attacks could be estimated. Based on the 78 completed subjects, this procedure showed that with 252 subjects there is a 90% probability of reaching the required 67 AC-determined attacks.

Within each AQP4-IgG stratum, randomization will also be stratified by region (Japan vs non-Japan). The number of Japanese subjects will be determined primarily by feasibility and will not depend on a minimum number of NMO/NMOSD attacks to be observed from Japanese subjects.

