The current study is being planned to detect a target relative reduction of 60% in risk for time from Day 1 to onset of AC-determined NMO/NMOSD attack on or before Day 197 with at least 90% power and $\alpha = 0.05$ (two-sided). A total of 67 AC-determined NMO/NMOSD attacks are required for the ITT population. Subjects will be randomized in a 3:1 ratio to receive either MEDI-551 or placebo within both AQP4-IgG seropositive and seronegative strata. The stratification ratio is anticipated to be approximately 80:20 with higher allocation to the seropositive cohort. If the seropositive cohort has 80% of the attacks, the study will have approximately 82% power to detect the target relative reduction of 60%.

Two hundred and fifty-two subjects will be randomized and dosed. This sample size is based on a blinded review of the attack rate for the first 78 subjects to complete the RCP and a simulation based on these subjects that indicates a > 90% probability of achieving the required 67 AC-determined attacks with 252 subjects.

Within each AQP4-IgG stratum, randomization will also be stratified by region (Japan versus non-Japan). The number of Japanese subjects will be determined primarily by feasibility and will not depend on a minimum number of NMO/NMOSD attacks to be observed from Japanese subjects. The study may conclude enrollment regardless of the number of subjects in Japan versus non-Japan regions.

Interim Analysis

An unmasked interim analysis will be conducted for futility assessment by an independent Data Monitoring Committee when approximately 34 AC-determined NMO/NMOSD attacks occur in this study. The study may be declared as “futile” if calculated predictive power at interim is < 20%.

TABLE OF CONTENTS

1	INTRODUCTION	18
1.1	Disease Background	18
1.2	MEDI-551 Background	19
1.3	Summary of Nonclinical Experience.....	20
1.4	Summary of Clinical Experience.....	21
1.5	Rationale for Study	22
1.6	Research Hypotheses	23
1.6.1	Primary Hypothesis	23
1.6.2	Secondary Hypotheses.....	23
2	OBJECTIVES.....	23
2.1	Objectives	23
2.1.1	Primary Objective	23
2.1.2	Secondary Objectives	23
2.1.3	Exploratory Objectives	24
2.2	Study Endpoints.....	24
2.2.1	Primary Endpoint.....	24
2.2.2	Secondary Endpoints	24
2.2.3	Exploratory Endpoint(s)	25
3	STUDY DESIGN	25
3.1	Description of the Study.....	25
3.1.1	Overview.....	25
3.1.1.1	Screening Period.....	28
3.1.1.2	Randomization (Day 1).....	28
3.1.1.3	Randomized-controlled Period (Day 1 to Day 197).....	28

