4.8.9 Control of Type I Error

The study is designed to strongly control the overall Type I error rate of $\alpha = 0.05$ based on the Bonferroni-based chain procedure (Bretz et al, 2009; Millen and Dmitrienko, 2011). The primary null hypothesis will be hierarchically tested first at $\alpha = 0.05$ in the AQP4-IgG seropositive cohort, and, if significant, it will be further tested in the ITT population at $\alpha = 0.05$. If and only if the treatment group comparison is statistically significant within the ITT population, secondary hypotheses will be tested. Null hypotheses for the 4 key secondary endpoints will follow the same sequential testing strategy as the primary analysis (testing within seropositive subjects first, followed by the ITT population if the comparison within seropositive subjects is statistically significant). Each secondary hypothesis will be initially tested based on the Bonferroni method at $\alpha = 0.05/4 = 0.0125$. If the null hypothesis for a particular secondary endpoint is rejected across both the seropositive and the ITT populations, the Type I error saved will be propagated equally to other non-rejected sets of secondary null hypotheses. The testing procedure will be repeated until all null hypotheses are rejected or no further null hypothesis can be rejected. Details are described in Appendix 11.

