Appendix 9 Sample Size Calculation

The proposed study is being planned to detect a target relative reduction of 60% in risk for time (days) from Day 1 to onset of an AC-determined NMO/NMOSD attack on or before Day 197 with 90% power and $\alpha = 0.05$ (two-sided), assuming an unequal randomization ratio of 3:1 to MEDI-551 versus placebo. Using the following formula, a total of 67 AC-determined NMO/NMOSD attacks will be required:

$$E = \left[\frac{z_{1-\alpha/2} + z_{1-\beta}}{\ln(HR)} \right]^2 \times \frac{(r+1)^2}{r},$$

where $z_{1-\alpha/2}$ and $z_{1-\beta}$ are 100(1 - α /2)th and 100(1 - β)th percentile of a standard normal distribution, $r = 3$ is the randomization ratio and $HR =$ hazard ratio = 0.4.

Assuming hazard rates of 1.5/year and 1.0/year for an NMO/NMOSD attack in the placebo arm for seropositive and seronegative groups, respectively, and using the following formula:

$$N = \frac{E}{\Pr(\text{Fail})},$$

a total of 212 (with an upward adjustment) subjects are expected to be enrolled in this study where

$$\Pr(\text{Fail}) = s_1 P_1 + s_2 P_2$$

is the weighted average of the failure probabilities P_1 and P_2 in seropositive and seronegative cohorts, respectively, with associated stratum specific weights $s_1 = 0.8$ and $s_2 = 0.2$. Recall that subjects will be enrolled to seropositive and seronegative cohorts in an 80:20 ratio.

Furthermore, the probability of an attack within i^{th} cohort ($i = 1, 2$) is given by

$$P_i = (1 - w)p_{i0} + wp_{i1}$$

the weighted average of the failure probabilities p_{i0} and p_{i1} for placebo and MEDI-551 groups, respectively; $p_{i0} = 1 - e^{-\lambda_{i0}F}$, $p_{i1} = 1 - e^{-\lambda_{i1}F}$; $F = 197/365 = 0.54$ to indicate the 197 days (28 weeks) duration of the controlled portion of the study; note that based on the assumptions for this study, $\lambda_{10} = 1.5$, $\lambda_{11} = 0.6$, $\lambda_{20} = 1$ and $\lambda_{21} = 0.4$ and $w = \frac{r}{1+r} = 0.75$.

Since the primary endpoint will be tested using the Cox proportional model, a simulation approach was used to investigate the power under alternative hypotheses mentioned above. Based on 5,000 simulations, the power for the overall and seropositive populations were observed as 94% and 91%, respectively. Moreover, the total required 67 events (212 subjects) were, on an average, distributed in seropositive and seronegative cohorts as 57 (168 subjects) and 10 (44 subjects) respectively.

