where $Z(t)$ is the observed Z -statistic at the interim futility analysis, t is observed information fraction and $Z_{\alpha/2}$ is upper $\alpha/2$ *th* quantile from standard normal distribution, and $\alpha=0.05$ ([Lan et al., 2009](#)). The $Z(t)$ will be calculated by the square root of the chi-squared statistic obtained from the aforementioned Cox proportional hazard model for the AQP4-IgG seropositive cohort and the ITT population, respectively. The observed information fraction t will be calculated using the observed number of AC-determined attacks at the interim analysis (ITT or seropositive) divided by the planned total number of AC-determined attacks for RCP (eg, 67 AC-determined attacks in the ITT population and 57 AC-determined attacks in the AQP4-IgG seropositive cohort for RCP).

The study may be declared as “futile” if

- the calculated predictive power is < 20% in the ITT population; AND
- the calculated predictive power is < 20% in the AQP4-IgG seropositive cohort.

If the study is declared futile the primary endpoint analysis and key secondary endpoint analyses will be conducted and all other endpoints will be summarized.

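### The stated 90% power is for the ITT test standing alone; the plan gives no power for the gated sequence and two unreconciled powers (82% and 91%) for the seropositive gate

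*Protocol*

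**What the plan says.** The synopsis plans for a 60% risk reduction "with at least 90% power"; Protocol 4.8.2, Appendix 9, SAP 2.4 and SAP Appendix 1 say 90%. All rest on 67 adjudicated attacks, which 4.8.2 and SAP 2.4 tie to the ITT population.

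The ITT test is not run unconditionally. The primary hypothesis is tested first in seropositive subjects and, under Protocol 4.8.9, "if significant, it will be further tested in the ITT population". Protocol Appendix 11, SAP Section 4 and SAP Appendix 3 give the same order. Rejection in the ITT population then opens the four key secondary endpoints.

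For the gating test the documents give two figures. Protocol 4.8.2 and SAP 2.4 say that, if 80% of attacks are seropositive, "the study will have approximately 82% power to detect the target relative reduction of 60"%. Protocol Appendix 9 reports from 5,000 simulations that "the power for the overall and seropositive populations were observed as 94% and 91%, respectively", with on average 57 seropositive attacks among 168 subjects and 10 seronegative attacks among 44. That simulation used 212 subjects; the current maximum is 252. SAP Appendix 1 repeats it but labels the text as the history of the 212-subject sizing. Protocol Appendix 9 has no such label beside the 91%.

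SAP Section 5 uses "57 AC-determined attacks in the AQP4-IgG seropositive cohort for RCP" as the planned total for the seropositive information fraction.

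**The concern.** Under this order the chance of rejecting in the ITT population cannot exceed the chance of rejecting in the seropositive cohort. A gate at about 82% therefore cannot coexist with a 90% chance of an ITT claim on the same basis. The ITT result is also the only route to the secondary endpoints, so its probability under the sequence is the one a reader of the synopsis needs, and neither document reports it.

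The gate has two powers nine points apart with no explanation. A reader cannot tell which applies at 252 subjects and 67 attacks, or whether the 90% target survives the gate.

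**Working it through.** **Inputs.** From Protocol 4.8.2, 4.8.3.1 and Appendix 9: HR 0.4, two-sided alpha 0.05, 3:1 allocation (r = 3), 67 attacks, 80:20 serostatus, placebo hazards 1.5 and 1.0 per year, 197 days of follow-up. The power calculation gives no dropout rate, so none is applied here.

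**Reproducing the plan.** Attacks required = [(1.960 + 1.282)/ln 0.4]² × 16/3 = 66.75, rounded up to 67. This matches.

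Inverted, power = Φ(√(E × 3/16) × 0.916 − 1.960):

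- E = 67: Φ(3.248 − 1.960) = 90.1%. Matches 90%.
- E = 0.8 × 67 = 53.6: Φ(2.905 − 1.960) = 82.8% (82.3% at 53). Matches about 82%.
- E = 57: Φ(2.996 − 1.960) = 85.0%. Does not match 91%.

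**Both tests on the same formula.** The two statistics share the seropositive attacks, so their correlation is √(seropositive attacks/67): 0.894 at 53.6 and 0.922 at 57. From the bivariate normal, the probability that both cross 1.960 is 81.5% at 53.6 and 83.7% at 57. The shortfall from the stand-alone 90.1% is 8.6 or 6.4 points. On this formula, 90% for both tests would need about 86 attacks at an 80% seropositive share, or 81 at an 85% share.

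**Both tests by Cox simulation.** Exponential hazards, HR 0.4, 3:1, serostatus as covariate in the ITT model, 5,000 runs per row. The Monte Carlo standard error near 90% is √(0.9 × 0.1/5,000) = 0.4 points. Rows that stop at the 67th attack assume uniform accrual over three years; the documents give no accrual pattern.

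| Set-up (seropositive + seronegative) | Mean attacks, seropositive/total | Seropositive | ITT alone | Both |
|---|---|---|---|---|
| 168 + 44, planning hazards, full follow-up | 58.2 / 69.2 | 91.9% | 94.9% | 91.0% |
| 168 + 44, planning hazards, stop at 67 | 54.9 / 65.3 | 90.5% | 94.4% | 89.6% |
| 202 + 50, planning hazards, stop at 67 | 56.8 / 67.0 | 91.0% | 94.5% | 90.3% |
| 155 + 39, placebo hazard 1.5 in both strata | 53.7 / 67.2 | 89.2% | 94.4% | 88.3% |
| 202 + 50, placebo hazard 1.08 in both strata | 53.9 / 67.4 | 90.0% | 94.9% | 89.4% |

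The first two rows agree with Appendix 9's 91% and 94%. The last two set the hazards so that about 80% of attacks are seropositive.

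Two further checks used 252 subjects and planning hazards. A set of 2,000 runs capped at 67 attacks gave 88.9% (standard error 0.7). A set of 30,000 runs, with accrual over two, three or four years and either a hard stop or 14 more days of follow-up, averaged 90.2% (standard error 0.2).

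**Source of the nine-point gap.** Going from 53.6 to 57 attacks moves the formula from 82.8% to 85.0%, about 2 points. The rest is method: for this HR and allocation the closed formula is conservative relative to the Cox simulation.

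**The case against.** The strongest reply is that the plan does not rest on the closed formula. Appendix 9 turns to simulation because the endpoint will be analysed by a Cox model, and by simulation the gated claim has about 90% power. The 82% is explicitly conditional on an 80% share and sits in the same paragraph as the 90%. The testing order is stated openly, and the 90% is tied to attacks required for the ITT population, which is a marginal power. Enrolment has already been stopped (Protocol Section 9, Amendment 6), so no sizing decision now depends on these figures.

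Most of this stands, and it limits the point. It rules out several stronger readings that a reader might infer:

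- *The trial falls short of 90% on any method.* The simulated joint power is within noise of 90%; the shortfall of 6 to 9 points belongs to the formula.
- *82% or 91% is a miscalculation.* Each reproduces on its own basis.
- *Joint power is the product of the two powers, about 75%.* The tests are correlated at about 0.9, so the product is wrong.
- *The 57 in the futility fraction is an error.* It agrees with the planning model, which gives about 57 of 67 attacks; 53.6 is the separate 80% scenario.
- *Type I error is affected.* It is not; this concerns power only.

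What the reply does not answer is that no section gives a power for the sequence, and that two powers for the gate stand side by side, by different methods, without saying so.

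**Conclusion.** The point holds as a reporting fault of limited size. The 90% at 67 attacks is a stand-alone ITT power, although the ITT test can run only after the seropositive test succeeds. On the formula that produced 67 and 82%, the chance of passing both is 81.5% (83.7% with 57 seropositive attacks), so 90% is clearly missed on that basis. Under the planning hazards the Cox simulation gives about 89 to 90% at 252 subjects and 67 attacks, and about 88 to 89% with an 80% seropositive share, so the target is roughly met there. The synopsis wording of at least 90% is not secure for the gated claim on either basis, but the simulated difference is too small to call a deficit.

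The seropositive powers of 82% (formula, 53.6 attacks) and 91% (Cox simulation, about 57 attacks, 212 subjects) are both correct on their own terms and unreconciled.

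These results assume HR 0.4 in both strata, exponential attack times, no dropout and the accrual patterns stated above.

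**What to change.** In the Protocol synopsis, 4.8.2 and Appendix 9, and in SAP 2.4 and Appendix 1:

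1. Label 90% as the power of the ITT test alone, and drop "with at least 90% power" from the synopsis or qualify it in the same way.
2. Add the probability of passing both primary tests by one named method, preferably Cox simulation at 252 subjects and 67 attacks (about 90% here), with its accrual and dropout assumptions.
3. Give one seropositive power with its method and attack count, from that same simulation. Keep 82% only if it is labelled as the conservative formula value for an 80% share of attacks.
4. In Protocol Appendix 9, mark the 94% and 91% as results for the superseded 212 subjects, as SAP Appendix 1 already does.

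In SAP Section 5 the 57 need not change; state that it comes from the planning simulation.

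The cost is wording plus one simulation run. Patients, alpha, tests and decision rules are unchanged; the stated power for an ITT claim becomes slightly less favourable. With enrolment stopped, the benefit is an accurate planning record.

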4.8.3 Efficacy

4.8.3.1 Primary Efficacy Analysis

The following are the null and alternative hypotheses associated with the primary endpoint:

$$H_{01}: HR^+ = 1 \text{ vs } H_{11}: HR^+ \neq 1,$$

$$H_{02}: HR^{ALL} = 1 \text{ vs } H_{12}: HR^{ALL} \neq 1,$$

where HR^+ indicates the hazard ratio of AC-determined NMO/NMOSD attack for MEDI-551 relative to placebo in AQP4-IgG seropositive subjects. HR^{ALL} denotes the same quantity for the ITT population. The treatment effect in the seropositive cohort will be defined as the relative reduction in HR^+ ; ie, $100 \times (1 - HR^+)$. A value of $HR^+ < 1$ or a positive value of relative reduction will indicate the efficacy of MEDI-551 compared to placebo in the seropositive cohort. Similar interpretations will hold for HR^{ALL} . For the current study, the target treatment effect of 60% implies a hazard ratio (HR) of 0.4.

For the AQP4-IgG seropositive cohort, the treatment effect will be assessed using the Cox proportional hazards model with treatment indicator (MEDI-551 or placebo) as an explanatory factor; whereas for the ITT population, the model will also include serostatus as an additional explanatory factor. The HR of MEDI-551 versus placebo will be estimated together with its associated 95% confidence interval (CI). The SAS PROC PHREG will be used for fitting this model. Subjects who complete Day 197 of the RCP or discontinue the study before Day 197 for reasons other than an AC-determined NMO/NMOSD attack will be censored in this model at the time of the Day 197/discontinuation visit. See Section 4.8.9 for details regarding Type I error control.

An indicator variable for Japan versus non-Japan region will not be included in the Cox regression model due to the low number of anticipated Japanese subjects. An evaluation of

consistency of treatment effect in Japanese subjects with that observed in the global study will be determined.

The data cutoff date for the primary analysis will be when the last subject completes the discontinuation visit following the 67th AC-determined attack, after all subjects complete the RCP if 67 AC-determined attacks do not occur, or after all subjects complete the EDV following discontinuation of enrollment upon recommendation of the independent DMC based on evidence of efficacy and safety. Subjects who are in the RCP when a total of 67 AC-determined NMOSD attacks have occurred or when enrollment is discontinued upon recommendation of the DMC based on evidence of efficacy and safety will discontinue the RCP as outlined in Section 4.5.1.2.

Since some AC-determined attacks may not be assessed within the assessment windows, a broader window will be used for primary analysis. Only AC-determined attacks with an assessment visit scheduled within 120 hours (5 days) of reporting symptoms and all assessments done within 10 days of an Assessment Visit will be included in the primary analysis. AC-determined attacks not included in primary analysis will be included in other supportive analyses. Sensitivity analysis will be conducted to assess the impact of the loss of any AC-determined attacks outside of the identified assessment window.

